6.2 Overall Survival

This will be measured from date of entry into study to date of death from any cause. Patients remaining alive or lost to follow up will be censored at the date of last follow up.

6.3 Disease free survival

This will be measured from date of start of CRT to time of documentation of local or metastatic tumour progression.

6.4 Quality of life

Quality of life will be evaluated at baseline and at each clinical oncology follow-up visit using the EORTC QLQ-C30 questionnaire. Late reactions will also be scored at each clinical oncology follow-up visit using the LENT/SOMA system for relevant normal tissues. A modified Inflammatory Bowel Disease Questionnaire and the Vaizey Incontinence Questionnaire will be used to assess bowel toxicity ^{23,24}. These will be assessed at initial assessment then 6 monthly.

6.5 Time to maximum tumour response

Time to maximum tumour response will be taken from completion of CRT to time when

stable but visible disease is demonstrated on 2 consecutive MRI scans.

6.6 Rectal surgery

The date of rectal surgery will be documented in the event of tumour regrowth. The type of rectal surgery will also be documented (sphincter sparing vs APER). The margin status of the resected specimen will be analysed.

7.0 FOLLOW UP

All patients will be followed up in clinic at regular intervals with CEA estimation at each clinic visit. Patients will be seen at 8-weeks post-CRT for review of 8-week results, DRE and EORTC QLQ-C30 completion (most patients will have been seen at 4-weeks, but for outside referrals, this, or a later appointment, may be a Registration visit). Patients will be followed after completion of all treatment every 3 months for 2 years, every 6 months for 3 years, and then annually until 10 years have elapsed. A follow-up proforma should be completed at each follow-up appointment, Please see Appendix 10.5 for full details of out-patient, MRI, CT, PET and flexible Sigmoidoscopy/colonscopy follow-up. A trial Pro Forma will be completed for all DRE's and Sigmoidoscopies. Colonoscopies are recommended as per NICE guidance²⁵. Radiology proformas will be completed by [name] and [name] at the time of central review. All proformas should be faxed to the RMH GI Clinical Trials unit as soon as possible ([contact]).

A number of patients will be recruited following a surgical 'second opinion' (usually regarding sphincter preservation). It is emphasized that the initial Surgeon (the Surgeon that performed the diagnostic biopsy) will be respectfully requested to perform all surgical follow-up, including sigmoidoscopies as per protocol. A standard letter will be sent after accrual to the initial Surgeon, and to the referring Clinical Oncologist. It is acknowledged that the involvement of the initial Surgeon is essential for the successful running of this trial. It is further acknowledged that there is a possibility that some initial Surgeons may disagree with recruitment into this trial, and thus may not wish to be involved in follow-up. In such situations, unless the Investigator can appoint a suitable alternative Surgeon to take over surgical follow-up and endoscopy (if possible a trial Investigator), the patient will not be eligible for accrual into this trial.

Patients that have not yet achieved a Tumour Regression Grade 1 or 2 on MRI at 8 week following completion of RT / CRT will have identical follow-up until grade 1 or

2 has been achieved (if stable disease is demonstrated for such a patient on 2 consecutive scans during this period, the patient will be referred for immediate surgery). More frequent MRI scanning will be performed at the discretion of the MDM. A modified Mandard Tumour Regression Grade has been used for reporting (please see appendix 10.2).

The timing, indication and interpretation of biopsies is viewed as critically important in the context of this trial. Blind biopsies are discouraged, ie if there is no abnormality on sigmoidoscopy/ colonoscopy, then we do not recommend biopsies directed at the mucosa once occupied by the tumour. Biopsies are discouraged unless: i) an area of residual disease is visualised at (and no earlier than) 3-month Sigmoidoscopy; ii) a clinically suspicious area develops/re-appears at Sigmoidoscopy/colonoscopy; iii) MR changes raise the suspicion of recurrence.

Patients with evidence of clinical or radiological local recurrence will be referred immediately by phone and fax to the surgical team for urgent biopsy. It is anticipated that such concerns will be brought to light by MR imaging, and thus will automatically be discussed at the Unit MDM. If there is a clinical suspicion of recurrence from a source other than MR, then an urgent MRI will be considered depending on date of previous imaging. All such cases will be discussed at the next available MDM. If urgent salvage surgery is recommended, a PET/CT scan will be performed routinely pre-op to outrule occult metastatic disease.

Subjects with metastatic disease detected during follow-up will be treated according to the Unit MDM recommendation.

Patients with evidence of clinical or radiological local recurrence must be treated at least as urgently as a primary rectal cancer by the surgical team.

8.0 STATISTICAL CONSIDERATIONS

Analysis methods

All time-to-event endpoints will be measured from the end date of chemoradiotherapy, and calculated using Kaplan-Meier methods. The final analysis will be carried out when all patients have had at least 2 years follow-up. An additional overall survival analysis may be carried out after all patients have had at least 10 years follow-up. **Patients who have not yet experienced the event in question will be censored at date of last follow-up**.

Primary endpoints

Since all patients will have at least two years complete follow-up, the percentage of patients in continued response without surgery at two years, and the percentage of patients with local failure at two years, will be calculated as percentages of all patients, with exact 95% binomial confidence intervals.

Secondary endpoints

Time to distant disease will be measured as the time to the first diagnosis of lymph node or other distant disease, confirmed via PET/CT, MRI, CT or pathology.

Time to maximal tumour response will be defined as follows: for patients who achieve CR, it is the time until first recorded MRI scan with tumour grade T0. In patients where this has not happened, it will be the time to the first of two consecutive MRI scans which show the same modified Mandard regression grading (or the first of two consecutive scans in which the second scan shows an increased Mandard regression grade). Patients with a continuing reduction in Mandard grade at the time of analysis will be censored at the date of last scan..Patients who opt for surgery or withdraw for other reasons before recorded maximal response will be censored at date of last scan.

Time to local regrowth will be measured as the time until the first recorded increase in Mandard grade, on MRI. Patients with continued stable disease or complete response will be censored at date of last MRI scan. Patients who opt for surgery or withdraw for other reasons before recorded local regrowth will be censored at date of last scan.

Of all patients who had surgery for progression of local disease, the percentage with positive margins will be calculated, with an exact 95% confidence interval. The percentage who had negative margins and had their sphincters preserved will also be calculated with an exact 95% confidence interval

Progression free survival will be measured as time until the first occurrence of any of the following: increased Mandard grade (in patients who did not achieve CR), any tumour T1 or above (in patients who achieved CR), first diagnosis of nodal or distant disease (diagnosed on MRI, CT, PET or pathology); or death from any cause.

Quality of life will be measured using EORTC QLQ-C30, IBDQ and Vaizey questionnaires. Missing data will not be replaced, but numbers assessed at each time-point will be reported. Change from baseline will be assessed at each time-point and summarised using descriptive statistics. In addition, counts and percentages of LENT-SOMA worst grades at each time-point will be reported.

Sample size

We wish to show that the percentage of patients who can successfully omit surgery is at least 10%, with a true rate expected to be at least 25% (and possibly this may be considerably higher). The two-year failure rate is assumed to be no more than 5%, and a failure rate of 15% or more would be considered to be unacceptable.

Using a single-stage exact phase II design, with one-sided significance level of 0.05, then a total of 59 patients would provide 80% power to prove a 2-year failure rate of less than 15% if the true rate is no more than 5%. The trial would be a success according to this endpoint if no more than 4 patients out of 59 have local failure at 2 years. The same number of patients would provide at least 90% power to show that the proportion of patients safely omitting surgery is more than 10%, if the true rate is

expected to be at least 25%. The trial would be a success according to this endpoint if at least 11 out of 59 patients have safely omitted surgery. To be judged a success overall the trial must pass both of these endpoints (no more than 4 patients with local failure, and at least 11 safely omitted surgery).

We expect to recruit 39 patients from the Royal Marsden and network hospitals and 20 patients from other multi-centre sites. This recruitment is expecting to be completed by 31st December 2012. We believe 60% of eligible patient will wish to participate in the "deferral of surgery". However, only 20% of rectal patients who undergo pre-operative CRT will develop a complete response and meet the inclusion criteria.

Stopping Rule

The trial will be stopped if 5 patients develop disease which is surgically not

salvageable or incompletely excised. There will be continuous monitoring of all

patients as part of the regular TMG

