5.5 Molecular prognostic and predictive markers of response	
to treatment substudy	15
5.6 Toxicity	16
5.7 Duration of Treatment	17
5.8 Pre-Registration Evaluation	17

5.9 Consenting Process	17
5.10 Adjuvant Chemotherapy	17
5.11 Adverse Events	18
5.11.1 Adverse events not subject to reporting	18
5.12 End of Trial Definition	18
	10
6.0 Assessment of Efficacy	18
6.1 Local Recurrence/Tumour regrowth	. 18
6.2 Overall Survival	19
6.3 Disease-free Survival	19
6.4 Quality of Life	19
6.5 Time to maximum tumour response	19
6.6 Rectal Surgery	19

7.0 Follow Up	19
8.0 Statistical Considerations	21
9.0 References	23
 10.0 Appendix. 10.1 Response Evaluation Criteria in Solid Tumours. 10.2 Modified Mandard Tumour Regression Grade. 10.3 PET/CT Central review. 10.4 MRI Method / Data Sheet . 10.5 Follow-Up Schedule. 10.6 LENT-SOMA. 10.7 FOPTC OOL 	25 25 26 27 43 51 53 57
10.7 Eok TC QOL 10.8 Vaizey Incontinence Questionnaire 10.9 MIBDQ	59 60

Fig. 1 'DEFERRAL OF SURGERY' TRIAL OUTLINE

- Rectal Cancer (T3/4, low T2 with threatened CRM, any N, M0)
- No pelvic side wall disease
- No local recurrence
- No metastatic disease
- Imaged on MRI

¥ Patients who have had am MRI performed more than 4 weeks following completion on CRT can also be included, with the next MRI/18F-FDG PET/CT scheduled 4 weeks afterwards. 18F-FDG PET/CT will be performed at 8 weeks, 16 weeks and 1 year following completion of CRT

* 'partial response' and stable disease' are defined by the RESCIST criteria, appendix 10.5

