Results from the trials outlined above support the safety of deferral of surgery for the evaluation of maximal tumour response after neo-adjuvant CRT. A non-surgical approach may be reasonable for those who maintain an apparent clinical and radiological response, with the term 'complete responders' reserved for those who achieve this response status with serial imaging and examination for at least 1 year after CRT.

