6.0 ASSESSMENT OF EFFICACY

6.1 Local Recurrence Rate / Tumour Re-growth

Local recurrence rate in patients who have achieved a sustained clinical and radiological complete response will be measured from the end date of CRT to time of documentation of local tumour recurrence/regrowth. It is emphasized that the development, or progression, of metastatic disease does not constitute local failure.

Time to Tumour regrowth / tumour recrudescence in patients who have not achieved a sustained clinical and radiological complete response will be measured from the date of start of CRT to time of documentation of tumour regrowth.

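### Time origins in Sections 6 and 8 contradict each other, and counting from the end of CRT credits event-free time before registration, with no stated limit for late referrals

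*Protocol*

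**What the plan says.** **Origins.** Protocol Section 8, under analysis methods: "All time-to-event endpoints will be measured from the end date of chemoradiotherapy, and calculated using Kaplan-Meier methods". Section 6 differs:

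- 6.2, overall survival: "This will be measured from date of entry into study to date of death from any cause".
- 6.3, disease-free survival: "This will be measured from date of start of CRT to time of documentation of local or metastatic tumour progression".
- 6.1, first paragraph: "Local recurrence rate in patients who have achieved a sustained clinical and radiological complete response will be measured from the end date of CRT".
- 6.1, second paragraph, for patients without a sustained complete response: "from the date of start of CRT to time of documentation of tumour regrowth".

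**Entry.** Sections 4.0 and 4.1 tie eligibility to MRI at 4 and 8 weeks after CRT, so the usual entrant registers at about 8 weeks. The Fig. 1 footnote widens this: "Patients who have had am MRI performed more than 4 weeks following completion on CRT can also be included". Section 7.0, on the 8-week visit, adds "for outside referrals, this, or a later appointment, may be a Registration visit". Section 5.9 only recommends an MRI within 8 weeks for patients treated elsewhere. No latest registration time is given, and delayed entry is not mentioned.

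**Primary endpoints.** Endpoint 1 in Section 3.1 is read two years after the end of CRT. Endpoint 2 is read at two years without restating the origin; the end of CRT is inferred from endpoint 1 and Section 8. Section 8 computes both as proportions of all patients. Success needs at least 11 of 59 omitting surgery and no more than 4 of 59 with local failure.

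**The concern.** There are three linked problems.

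1. Section 8 covers every time-to-event endpoint, yet OS, DFS and one of the two regrowth measures have other origins in Section 6. An analyst cannot follow both sections.
2. A patient who regrew, developed metastases, had surgery or died before registration is never enrolled. A patient who does register has passed through that time without the event. Counting from the end of CRT credits this time to the trial population, and the credit grows with the delay to registration. It lowers the curves for regrowth, distant disease, PFS and death, and it helps both primary rules.
3. Section 6.1 selects patients by a response that must be maintained, but starts their recurrence clock before it could have been maintained.

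At stake are a clear definition of the secondary endpoints and the error rates of the two success rules.

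**Working it through.** **Step 1: gap between the clocks.** The lead centre gives 25 fractions plus a boost of 3 to 5 (Section 5.3), that is 28 to 30 fractions. At five a week this is 28/5 = 5.6 to 30/5 = 6 weeks. The two regrowth groups in 6.1 therefore run on clocks about six weeks apart.

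**Step 2: the plan's own design.** Exact binomial with n = 59:

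- Failure: P(X ≤ 4 | 0.15) = 0.047 and P(X ≤ 4 | 0.05) = 0.828. This is the smallest n with error at most 0.05 and power at least 80%, so 59 reproduces.
- Omission: P(X ≥ 11 | 0.10) = 0.031 and P(X ≥ 11 | 0.25) = 0.903, in line with the stated power of at least 90%.

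The sample size is not in error.

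**Step 3: share of the two-year window already passed at entry.** At 8 weeks: 8/104 = 7.7%. At 6 months: 6/24 = 25%. At 12 months: 12/24 = 50%.

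**Step 4: effect of late entrants on the success rules.** Assumptions, not protocol figures: the 10% and 15% limits describe patients selected at week 8 (1.85 months); the hazard is constant from then; late entrants are event-free at entry. For entry at month m, let e = (24 − m)/(24 − 1.85). The conditional two-year probabilities are then 0.10^e for omission and 1 − 0.85^e for failure.

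| Entry | e | Omission | Failure |
|---|---|---|---|
| 6 months | 0.8125 | 0.154 | 0.124 |
| 9 months | 0.677 | 0.210 | 0.104 |
| 12 months | 0.542 | 0.287 | 0.084 |

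With k late entrants and 59 − k standard entrants, the sum of unequal Bernoulli variables gives the one-sided error of each fixed rule at its limit:

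| k | Omission error, entry at 6 / 9 / 12 months | Failure error, entry at 6 / 9 / 12 months |
|---|---|---|
| 0 | 3.1% | 4.7% |
| 3 | 3.6 / 4.3 / 5.2% | 5.0 / 5.2 / 5.4% |
| 5 | 4.0 / 5.2 / 7.2% | 5.1 / 5.5 / 5.9% |
| 20 | 8.3 / 17.8 / 36.6% | 6.7 / 8.7 / 11.2% |

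The last row uses the 20 patients whom Section 8 expects from other sites, as an upper case.

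**Step 5: uniform 8-week entry.** If the limits refer to patients selected at week 8, nothing is inflated (3.1% and 4.7%). If they were meant to count from the end of CRT, the conditional probabilities are 0.10^(22.15/24) = 0.119 and 1 − 0.85^(22.15/24) = 0.139, and the errors become 8.8% and 7.2%. The protocol does not say which is meant.

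**Step 6: recurrence after sustained CR.** Section 2.4 keeps the term for complete responders "reserved for those who achieve this response status with serial imaging and examination for at least 1 year after CRT". If that duration governs the word *sustained* in 6.1, no first-year recurrence can appear on that curve. As an illustration, assume that three quarters of two-year regrowth falls in year 1. A true rate of 30% would then be reported as 1 − 0.70/(1 − 0.75 × 0.30) = 1 − 0.70/0.775 = 9.7%. True rates of 20% and 40% would be reported as 5.9% and 14.3%. A shorter duration gives a smaller understatement.

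**The case against.** Several points on the other side stand.

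- A reader might infer that the Section 6 origins distort the primary endpoints. They do not. Both are proportions of all patients; only late entry reaches them.
- A reader might infer that every curve carries guaranteed event-free time. OS under 6.2 starts at entry, and maximal response can occur before registration, because a T0 scan at 4 weeks counts.
- A reader might infer that 6.1 rules out first-year recurrence. Section 2.4 does not define *sustained*, and Section 5.9 uses the word for confirmation at the 8-week MRI. Regrowth without sustained CR is captured by the second paragraph of 6.1, and the regrowth endpoint in Section 8 has no such condition.
- A reader might infer a false-success rate near 37%. That needs all 20 other-site patients to enter at 12 months still in CR. Section 8 describes recruiting sites, not late referrals, and eligibility is built around the 4- and 8-week MRIs.
- The model treats omission as loss from a CR that everyone holds at week 8, whereas patients with a good partial response are eligible (Section 4.0) and may reach CR later. Overall success also needs both rules, so a single-endpoint error is an upper bound on false overall success when that endpoint is at its limit.
- DFS is not among the endpoints in Section 3.2, which lists progression-free survival.

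These points limit the size. They do not reconcile the origins, cap late registration or supply a rule for delayed entry.

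**Conclusion.** The concern holds in limited form. The contradiction between Section 8 and Sections 6.1 to 6.3 is plain on the text and touches secondary endpoints only. The credit for time before entry is also real: under Section 8 it affects regrowth, distant disease, PFS and OS, and through late registrants it affects both primary proportions in the favourable direction.

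The effect on the primary rules is small if late entry is rare. With 3 to 5 late entrants, omission error is 3.6-7.2% and failure error 5.0-5.9%, against 3.1% and 4.7%. It becomes serious only if late entry is common (8-37% and 7-11% with 20). All these figures rest on a constant hazard and assumed entry times. The recurrence measure in 6.1 understates early recurrence only to the extent that *sustained* requires a later period of response.

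**What to change.** 1. Delete the conflicting origins in 6.1 to 6.3 and state one origin, the end of CRT.
2. For regrowth, distant disease, PFS and OS, let each patient enter the risk set at registration (delayed-entry Kaplan-Meier). Keep time to maximal response from the end of CRT without truncation, since truncation would drop patients whose T0 scan came before registration.
3. Delayed entry does not apply to the binomial primary counts. For these, state a CRT-to-registration window, report both proportions with and without patients registered after it, and show the distribution of that interval. State endpoint 2's origin, and say whether the 10% and 15% limits refer to patients selected at about 8 weeks.
4. Measure recurrence after CR from the date CR is first recorded, or from a stated landmark, and define *sustained* once.

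The cost is wording plus two dates, end of CRT and registration; the second already arises from the procedure in Section 4.3. Fewer patients will be at risk early on the curves, and the sensitivity result may be less favourable. Delayed entry also assumes that the time of registration is unrelated to later risk. The window and origin should be set before outcomes are analysed.

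### PFS and time to distant disease are censored at last follow-up although their non-death events need imaging or pathology; two sister endpoints are censored at last scan, so both curves can read too high

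*Protocol*

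**What the plan says.** All of the following is in Protocol section 8.0 unless stated otherwise.

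- **General rule for time-to-event endpoints:** "Patients who have not yet experienced the event in question will be censored at date of last follow-up". The estimator is Kaplan-Meier, with time counted from the end of chemoradiotherapy.
- **Time to local regrowth** (first rise in Mandard grade on MRI) has its own rule: "Patients with continued stable disease or complete response will be censored at date of last MRI scan".
- **Time to maximal response** also has its own rule: "Patients with a continuing reduction in Mandard grade at the time of analysis will be censored at the date of last scan". For both of these endpoints, patients who opt for surgery or withdraw are likewise censored at the last scan.
- **Time to distant disease** has a definition but no censoring rule: "Time to distant disease will be measured as the time to the first diagnosis of lymph node or other distant disease, confirmed via PET/CT, MRI," and the list goes on to name two more accepted routes, a CT scan and pathology.
- **PFS** has a definition but no censoring rule. Its local part is "increased Mandard grade (in patients who did not achieve CR), any tumour T1 or above (in patients who achieved CR"); the rest is "first diagnosis of nodal or distant disease (diagnosed on MRI, CT, PET or pathology); or death from any cause".
- **Overall survival** (section 6.2) is censored at last follow-up.

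Section 7.0 runs clinic follow-up to 10 years and refers to Appendix 10.5 for "full details of out-patient, MRI, CT, PET and flexible Sigmoidoscopy/colonscopy follow-up". That appendix is not in the text available to me.

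**The concern.** Section 8.0 uses the last scan as the censoring date for two endpoints that are read on MRI, so it treats the last scan and the last follow-up as different dates. PFS and time to distant disease also depend on imaging or pathology, but they fall back on the general rule. A patient last scanned at 12 months and last seen at 36 months leaves the regrowth risk set at 12 months but counts as progression-free until 36, although the same MRI grade rise is an event for both.

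The gap between the two dates is plausible in this trial. Clinic follow-up lasts 10 years, while section 5.4 plans PET/CT usually three times, the last at 1 year. Surgical follow-up is requested from the initial surgeon, while patients treated elsewhere have their imaging at the lead centre (sections 5.9 and 7.0). Contact can therefore continue after imaging has lapsed. In a single-arm study asking whether surgery can be deferred safely, the error would flatter deferral.

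**Working it through.** **1. The plan's own figures.** The protocol gives no figure for PFS or distant disease. Its design figures reproduce by exact binomial calculation:

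- Local failure, at most 4 of 59: one-sided error 0.0469 at a 15% rate, power 0.828 at 5%.
- Surgery omitted, at least 11 of 59: error 0.0306 at 10%, power 0.903 at 25%.

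These are percentages of all patients. No censoring date enters them.

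**2. Direction.** The Kaplan-Meier estimate is the product of (1 - d/n) over event times, with d events among n at risk. Moving a censoring date from the last scan to a later visit leaves every d unchanged and can only raise n. The curve stays the same or rises.

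**3. Size.** The documents give no event rates and no missed-scan rates, and the imaging schedule is not shown. The inputs below are assumptions:

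- true 2-year PFS of 65%, constant hazard;
- a share f of patients stops imaging at month 12 but attends clinic to month 36;
- a share c of the later progressions in those patients is found clinically and confirmed.

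Then S(12) = 0.65^0.5 = 0.8062, S(24) = 0.65 and S(36) = 0.65^1.5 = 0.5240.

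*Written rule.* Nobody is censored before month 24, so the estimate is S(24) + f(1 - c)[S(12) - S(24)] = 0.65 + f(1 - c) × 0.1562. With c = 0:

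| f | Written rule | Excess over 65% |
|---|---|---|
| 0.1 | 66.6% | 1.6 points |
| 0.2 | 68.1% | 3.1 points |
| 0.3 | 69.7% | 4.7 points |

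*Strict last-scan rule.* Unimaged patients leave at month 12 unless their progression is found. Just after month 12:

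- at risk: n = (1 - f)S(12) + f·c·[S(12) - S(36)];
- events by month 24: e = (1 - f + f·c)[S(12) - S(24)];
- estimate: S(12)(1 - e/n).

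With f = 0.2:

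| c | Written rule | Last-scan rule |
|---|---|---|
| 0 | 68.1% | 0.8062 × (1 - 0.1250/0.6450) = 65.0% |
| 0.5 | 66.6% | 0.8062 × (1 - 0.1406/0.6732) = 63.8% |
| 1 | 65.0% | 0.8062 × (1 - 0.1562/0.7014) = 62.7% |

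Simulation with 3-monthly scans agrees within sampling error.

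**4. Wider assumptions.** A second simulation let 10-30% of patients stop imaging at random between months 3 and 24, with scans every 3 to 12 months, 2-year event rates of 20-40% and no clinical detection. The written rule read about 1 to 8 points above last-scan censoring. With imaging kept up in everyone, the difference at 2 years was 0.

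**The case against.** The strongest objection is that clinic follow-up here is active surveillance. Section 7.0 provides CEA at each visit, and DRE and sigmoidoscopy with their own proformas. Clinical evidence of local recurrence leads to referral for urgent biopsy, and an urgent MRI is considered. Pathology counts for both endpoints, the T1-or-above criterion names no modality, and death is a PFS event. A reader might infer that a patient who is no longer imaged cannot have an event recorded. The documents do not support that, and the sizes at c = 0 are an upper case within the scenario in step 3.

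A reader might also infer that censoring strictly at the last scan would put things right. It does so only at c = 0. When scans are prompted by suspicion, cases stay in as events while well patients leave the risk set. With f = 0.2 and half of the progressions found, the written rule is 1.6 points too high and the strict rule 1.2 points too low. With all found, the written rule is right and the strict one is 2.3 points too low. This part of the objection stands and shapes the fix.

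Three further points carry less weight:

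- Last follow-up could be read to include imaging. The separate use of last scan in the same section, and of last follow-up for overall survival, speaks against that reading.
- The 10-30% share is assumed, and section 8.0 expects complete follow-up for two years. This limits the size but does not remove the inconsistency.
- Censoring dates are often left to the SAP. Here, however, the protocol states a rule and applies it unevenly.

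**Conclusion.** The point holds as an inconsistency in a stated rule, with an upward risk for two secondary endpoints. PFS and time to distant disease can read too high wherever disease assessment lapses while contact continues. At 2 years the effect is zero if imaging is kept up, about 1.5 to 5 points under the month-12 scenario with no clinical detection, and smaller with clinical detection. These sizes rest on assumed inputs. For scale, the 95% half-width at 65% with 59 patients is 1.96 × √(0.65 × 0.35/59) = 0.122, about 12 points. The shift is thus well inside the random error but runs in one direction.

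Two stronger readings should be resisted. A reader might infer that the trial's success decision is biased; it is not, because both primary endpoints are binomial percentages of all patients. A reader might also infer that the PFS curve will lie above the regrowth-free curve. It could, but PFS also counts nodal disease, distant disease and death, which pull it down, and nothing in the documents shows that the curves would cross.

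**What to change.** In section 8.0:

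- Limit the last-follow-up rule to overall survival.
- Censor PFS patients who are alive without progression at the date of the last disease assessment able to detect progression (MRI, CT, PET/CT, or endoscopy/biopsy). Deaths remain events; state how a death after a long gap without assessment is handled.
- Censor time to distant disease at the last imaging that covers distant sites (CT or PET/CT), not at a pelvic MRI alone.
- Report the last-follow-up version of both endpoints as a sensitivity analysis, because strict last-scan censoring can bias downwards when scans are prompted by clinical suspicion. The two versions together show how much the choice of date matters.

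The cost is a few sentences of text. Imaging is centrally reviewed with radiology proformas (sections 5.9 and 7.0), so scan dates should be obtainable, though the proformas are not shown. The downside is slightly less follow-up time and marginally wider intervals. Sample size and success rules stay as they are.
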